Whole lung clearance is strongly dependent on the site of particle deposition within the lung. To characterize regional deposition in the lung a transmission scan of the subject's lungs will be obtained on each MCC study day to outline the area of the whole lung. Central (C) vs. peripheral (P) deposition will be determined by region of interest (ROI) analysis and normalized to C/P for the transmission scan. A whole lung ROI bordering the right lung will be used to determine, by computer analysis, the whole lung retention, as a fraction of the initial counts in the right lung, over the two hour clearance period and at 24 hours. The computer program decay-corrects the Tc99m counts throughout the clearance period. Both C and P lung retention will also be determined to allow comparisons of MCC from a region with a preponderance of large, bronchial airways to a region lacking such airways.

10. Symptom Scores:

Subjects will be asked to rate a variety of possible symptoms during the dosing period, including the following: headache, irritation of the nose stuffy nose/sinus congestion, runny nose, dry/sore throat, pain on deep inspiration, unusual fatigue or tiredness, eye irritation, sneezing, shortness of breath, cough, wheezing/whistling in chest, chest tightness, sweating and other.

The following symptom score assessment will be made:

0 = NONE	(not present)
1 = TRACE/NOTICED	(barely detectable)
2 = MILD/LIGHT	(present, but not annoying)
3 = MODERATE	(present, but somewhat annoying)
4 = SEVERE/HEAVY	(present and very annoying and painful)

The highest possible score will be 60 and the lowest is 0. A mild score for every criteria is 15, moderate is 30 and severe is 60.

11. Venipuncture: Blood samples totaling approximately 50ml will be taken each week for a total of 150ml. An additional volume of 6ml will be taken during each O₃ exposure.

Observation Schedule: Prior to any inhalation challenge, subjects will undergo a physical examination of the ears, nose, throat and chest and will have an assessment of vital signs (temperature, pulse, respiratory rate, blood pressure), oxygen saturation, symptom score assessment and undergo spirometry to rule out acute illness prior to challenge. All female volunteers will undergo a urine pregnancy test. The timing for collecting study endpoints in relation to the exposure is that time 0 is when the subject enters the exposure chamber. Induced sputum will be obtained on the screening day and again at six hours after each exposure. Sputum will be analyzed for PMN content, CD14 expression on airway macrophages and monocytes, soluble CD14 levels, cytokine levels in sputum and products of inflammatory cells (eosinophil cationic protein, myeloperoxidase). Blood will be collected for a CBC and differential and other exploratory endpoints when the pre- challenge induced sputum is obtained and 6 hours after challenge.

Any subject who is asked to withhold ICS for the purpose of this study will have baseline asthma symptom scoring done. These subjects will complete scoring each day that they withhold medication. They will be given contact information for a study physician who will be available 24 hours a day. They will have rescue albuterol available. Subjects will be discontinued from the study and returned to prior dosing regimen if they have sustained increase in asthma symptoms. Subjects will be treated with prednisone if needed for an exacerbation.

Post-Challenge Observations Reporting:

All volunteers will be discharged home after each challenge day with contact information for a study physician.

Each volunteer will be given a symptom scoring sheet for each day up to 96 hours (4 days) after challenge. The following instructions will be written on the sheet:

Please record your symptom score today at noon based on the scale above. Please call the study coordinator or physician for the following reasons:

1. If your total score is >6 plus your baseline score.
2. If any of your individual symptoms equals 4.
3. If you are concerned about symptoms regardless of the score you assign them.

Each sheet will include the name and phone number of the study MD. Sample home symptom scoring sheets and instructions are included with this protocol.

Study discontinuation visit (Visit 7):

Within 5-10 days of the final challenge dose, each subject will be asked to return for a study discontinuation visit. At that time temperature, pulse, systolic and diastolic BP, respiratory rate, FVC and FEV1 and SpO₂ (oxygen saturation), CBC, PT and aPTT and symptoms scores will be assessed and, if abnormal, medical evaluation as directed by the study physician will be undertaken.

Definition of an unanticipated problem, or UP, (previously referred to adverse event AE) and Serious Adverse Event (SAE):

An unanticipated problem for a given volunteer will be defined as failure of any of the safety criteria outlined in section "d." Additionally, minor upper respiratory tract infections occurring within 96 hours of the exposure will be considered adverse events. Other, non-specified clinical illnesses, which occur within 96 hours of each challenge, will also be reported as an AE. Any decrease in lung function or increase in symptom score, as outlined in section "d" will be considered an adverse event. Failure of a total symptom score to return to no greater than 6 above baseline within 96 hours will be considered an adverse event. Any symptoms that induce a volunteer to seek medical attention from any provider within 96 hours of challenge will be considered an adverse event.

A significant adverse event will be defined as any event that requires hospitalization or results in, life threatening illness or injury, permanent (or likely to be permanent) illness or injury, or death if these events occur within 96 hours of challenge (or if the clinical scenario leading up to hospitalization, illness, injury or death begins within 96 hours of a challenge).

g. Monitoring and risk minimization

Risks to subjects: At the doses proposed in this study, the most significant predictable risk to subjects as a result of ozone inhalation is development of airway inflammation which would cause shortness of breath, cough or wheeze. Ozone is known to cause a temporary inhibition in the ability to take a deep breath – this is transient and typically declines within 2 hours of completion of exposure, though it may take up to 72 hours for complete resolution. At high doses, tocopherols can increase coagulability, though we have not observed this in other studies using gamma tocopherol. Nausea and upset stomach have been reported, subjects are asked to take the supplement with food. Sputum induction may induce bronchospasm. Venipuncture carries a risk for hematoma. There is a slight risk of sneezing with ELF collection, subjects who may not be able to tolerate the paper will not be asked to continue with this measurement. Nasal epithelial biopsy is a transiently irritating procedure, and it presents a rare risk of nose bleed.

Measures to minimize risk: Only volunteers who have normal lung function will be recruited for this project. Further, subjects will be deferred for challenge until 4 weeks after complete resolution of each of the following acute illnesses: viral respiratory tract infection, pneumonia or bronchitis requiring antibiotic therapy (must be off antibiotics and well for 2 weeks after the last dose of antibiotics, 4 weeks in the case of azithromycin due to its prolonged half-life), or acute illness resulting in fever. Also, unspecified illnesses, which in the judgment of the investigator increase the risks associated with ozone inhalation challenge, will be a basis for exclusion. As outlined above in section "d", all subjects will need to fulfill objective lung function and symptom criteria prior to initiating a specific challenge study. Subjects will be questioned about their previous radiation exposure history. Subjects whose exposure history

within the past twelve months would cause them to exceed their annual limits will be excluded. Upon being accepted into the study each subject will be advised to avoid radiation doses of a comparable magnitude within the next 12 months unless there is a diagnostic or therapeutic necessity. Female volunteers will be asked to use effective birth control and will provide a urine sample to test for pregnancy on study days. If the test is positive or the subject has reason to believe she may be pregnant, she will be dismissed from the study. Nasal samples will not be collected in subjects who have had recent nasal surgery.

Risks from MCC measures

The radiation doses for up to 120 μCi of inhaled Tc99m-SC (3exposures of 40 μCi over the three month period) to various organs (other than the lungs) are listed below:

ORGAN DOSE (mRem)

Kidneys	12
Bladder Wall	9
Stomach Wall	30
Thyroid(unblocked)	18
Testes	1.2
Ovaries	5.4
Red Bone Marrow	2.4
Upper Large Intestine	15
Lower Large Intestine	1
Whole Body	1.8

These doses were computed assuming an instantaneous uptake of free TcO4(99m) from the systemic circulation. This simulates the situation where all of the label breaks free from sulfur colloid and is transported instantaneously to the systemic circulation. These doses represent extreme cases that rarely, if ever, occur in practice. Previous studies show no Tc99m activity in the bloodstream of dogs over a 3 hour period after depositing Tc99m-sulfur colloid on the airway surfaces of dogs. TcO4(99m) is secreted by the gastrointestinal tract and there is minimal reabsorption. Thus, if all the label were to break free from the sulfur colloid, the stomach, large intestine, thyroid and kidney which see a large blood flow would receive the highest exposure from TcO4(99m). Since the sulfur colloid particles are not water soluble they are not cleared by dissolution.

For our inhalation conditions 30-60% of the inhaled particles will likely clear by mucociliary clearance. Particles that clear by this mechanism will be swallowed and eliminated by the GI tract. Most of the remaining deposited particles will be in alveoli or small airways and clear by much slower processes with a half-time of approximately 60 days. Considering the short physical half-life of Tc99m one need not consider the radiation doses to organs, other than the lungs and GI tract, from Tc99m bound to sulfur colloid. There is potential for enhanced radiation doses to large airway epithelia. The local radiation dose depends on the pattern of particle deposition and on the rate of mucociliary clearance. Using published data and assuming a mucus transport rate in the trachea of 1.0 mm/min (representing the lowest limit measured in normal humans), the highest radiation dose delivered to the trachea will be 0.8 Rems for a single 40uCi exposure. The radiation dose will decline towards the more peripheral portions of the lung reaching 0.016 Rems in the parenchyma or alveolar regions. The unweighted average dose to all tissue compartments will be 0.32 Rems (for a single 40uCi

exposure). These computed doses represent the upper limits since normal tracheal mucus velocity is approximately 5 mm/minute.

Transmission scans will also be obtained to identify non-ventilated lung regions.

These scans will be used to outline/define the whole lung regions for region-of-interest analysis of the Tc99m-SC radioaerosol scans on each study day. For the lung transmission scan procedure, a planar, solid sheet containing the radioisotope Co57 (< 25 mCi) will be placed in front (5cm from body) of the patient sitting with his/her back to the gamma camera while a 30 sec gamma camera scan is acquired. In this case the dose from the Co57 exposure is from an external source (i.e. not inhaled) and is similar over all portions of the lung tissue (i.e. similar to a chest X-ray). The dose to the surface of the chest and the lungs (assuming no chest wall attenuation) under these conditions is 7.5 mRad for a single scan, a relatively small dose compared to the inhaled radioaerosol. As the Co57 source decays over time (270-day half-life) we will increase the time for the transmission scan accordingly to achieve comparable scans of the lung while not exceeding the 7.5 mRad dose per scan.

The transmission scan has been used by us and others to provide a delineation of lung boundaries for assessing regional deposition/clearance of the inhaled radioaerosol. The absorbed radiation doses from the low activity (<1uCi) /energy (66Kev) Americium241 sources, placed on the subjects backs for alignment of images, is insignificant relative to the Tc99m and Cobalt57 doses associated with these experiments.

The maximum doses that we have computed for the lungs (combined three Tc99m and three Co57 transmission), 2.4 Rem local dose and 0.98 Rem average for whole lung, are well under the maximum single dose of 5 Rems for a normal adult volunteer as set forth in Federal regulations, and well under the 15 Rem maximum for the annual dose commitment. The doses to all other organs and the whole body are all far less than these maximum doses. **The total effective dose equivalent (based on the unweighted average to the whole lung of 983 mRem) is 133 mRem.** In considering these dose estimates and comparing it with other nuclear medicine procedures, it should be emphasized that we have gone to considerable lengths in calculating local tissue doses. Most often average doses to organs are used which would be considerably less than any local doses.

While the radiation exposure associated with our measures of MCC represents a potential risk to the human volunteers in this study, the risk is very low. The effective dose for the three measures of MCC (including Co57 transmission scans) is approximately 133 mRem. This is less than the natural environmental radiation that adults receive every year, which in Chapel Hill is about 300 mRems. The risk from the radiation dose received from this procedure is too small to be detected. In addition, the dose of Tc99m- sulfur colloid to be deposited in the lung for each measure of MCC is 10% of that recommended as the adult oral dose for diagnosing pulmonary aspiration by gamma scintigraphy (CIS-US, Inc).

A physician familiar with the protocol will be available for all challenge procedures. Emergency treatment with albuterol, oxygen, and oral corticosteroids will be available to those patients who require such therapy. The human exposure laboratory is also equipped with an emergency "crash cart" with standard emergency medications, IV fluids and a defibrillator in the unlikely event of a medical emergency for any challenge or exposure study.

All subjects will be monitored as outlined in previous sections and will return for assessment 24 hours after the challenge. All subjects will be provided with a contact telephone number for access to a study physician who is on call 24 hours/day.

Reporting of AEs and SAEs

All SAEs will be reported to the CBER of the FDA as well as to the UNC Biomedical Institutional Review Board (IRB) within 24 hours of recognition of the event. Adverse events will be reported to both the FDA and UNC IRB on an annual basis, or when the protocol is completed. If criteria for suspension of the protocol are met, then the FDA and UNC IRB will be notified within 24 hours.

All subjects with a non-fatal SAE will be evaluated medically by a study physician, in concert with their own physician as appropriate. Likewise all subjects with an unexpected problem related to the study will be evaluated by a study physician, and if needed the subject will be examined by the study physician. All assessments will include the same lung function and temperature assessments outlined for challenge observation. Other assessments will be undertaken as needed. Any unspecified event, which in the judgment of the PI of the study, constitutes an unusual, unexpected or prolonged event (greater than 96 hours) event will be reported to both the FDA and the UNC IRB.

CERTIFICATE OF ANALYSIS

No. 60-1399

Messrs.

17 Jul 2013

 タマ生化学株式会社
TAMA BIOCHEMICAL CO., LTD.
[name],
[name]

T a m a E - G 8 0

(*d*-gamma Tocopherol 80%)

Lot Number : 307111

Tests	Specifications	Results
Description	A light yellow to reddish brown, clear and viscous liquid, having a faint characteristic odor	Good
Identification	Red to orange color development	Passed
Acidity	Not more than 1.0 ml/g	0.1 ml/g
Heavy Metals (as Pb)	Not more than 10 ppm	Within Limit
Arsenic	Not more than 1 ppm	Within Limit
Transmittance	Not less than 20.0 % (550nm)	73.7 %
d -gamma Tocopherol	Not less than 80.0 %	90.0 %
Total Tocopherols	Not less than 90.0 %	94.7 %
Benzo(a)pyrene	Not more than 1.0 ppb	0.1 ppb
Aerobic Plate Count	Not more than 1000 cfu/g	Within Limit
Coliforms	Negative	Passed
Residual solvents	USP <467> only class 2 solvents	Within Limit

[figure not shown]
Evaluation Passed

Manufacturing Date : 11 Jul 2013

Expiry Date : 10 Jul 2016

Lead (random test) Not more than 2 ppm (FCC)

Study Title

Effect of Gamma Tocopherol Enriched Supplementation on Response to Inhaled O3 Exposure

NCT number NCT02911688

Document Date December 17th, 2019

Statistical Analysis Plan

For

Effect of Gamma Tocopherol Enriched Supplementation on Response to Inhaled O₃ Exposure

Statistical Analysis:

The effect of gamma tocopherol (γ T) on ozone (O₃) response of continuous variables (e.g., PMNs in sputum, cytokines, mucins) will be assessed using the difference pre O₃ values after γ T and placebo dosing for a given variable. To analyze cross-over clinical trial data, graphical presentations will be used to highlight potential order and treatment effects and use rigorous testing to confirm these effects. For these graphical presentations, the two plots that depict period 1 responses against period 2 responses for both arm sequence groups (Placebo-Active and Active-Placebo) will be examined to confirm the presence of absence of period effect. The response centroids of each sequence group will be calculated to determine if a direct treatment effect of γ T exists. These observations will be tested with a paired t-test or Wilcoxon signed rank test, depending on normality of the data, to evaluate the significance level of the treatment, the period and the carryover effects.

For analysis of mucociliary clearance outcomes, linear regression models will be fitted that account for the initial regional lung deposition of radioaerosol (the central-to-peripheral, or C/P, deposition ratio) as a covariate to determine if γ T treatment impacts O₃-induced changes in MCC compared to placebo. [name], the biostatistician for the CEMALB will lead the statistical team overseeing data analysis and guide the statistical analysis.

As an alternative analysis approach, regression modeling techniques will be employed to assess genotype effects (including the GSTM1 null genotype) on response to pollutants. For this study, a linear mixed model approach will be used that considers individual tests in a global, unified way where all data are used at the same time. This method should be more powerful than the two sample t-tests, especially when there is a significant carryover effect. This approach will also allow us to account for the influence of gender, race, BMI, and analysis of the effect of the GSTM1 null genotype on response to O₃ and effect of γ T on this response.

To address potential missing data, we will employ multiple imputation methods to address this issue when appropriate.

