d. Design of Study.

This will be an intention-to-treat study. The effect of gamma tocopherol (γT) on O₃ response of continuous variables (e.g., PMNs in sputum, cytokines, mucins and MCC) will be assessed using the difference (delta) from baseline (i.e. post -O₃ minus baseline) values, comparing γT versus placebo treatment periods,

Potential subjects will be seen for an initial visit at which time informed consent will be obtained. Once the subject is deemed eligible by clinical lab and sputum values, they will return to the research lab for treadmill training and baseline muco-ciliary clearance (MCC) lung scan including a lung transmission scan. Treadmill training is required to determine the treadmill settings for the exposure day, and will be done prior to MCC to control for exercise

effects on the baseline MCC measurements. Baseline nasal endpoints will also be collected to determine pre and post O₃ nasal epithelial cell gene expression levels and cytokine production. On the following day, subjects will return to the imaging lab for a 30-minute follow-up MCC scan.

Within 30 days of the screening visit, subjects will come in for randomization to placebo or gamma tocopherol (yT) supplement. At this visit, vital signs will be measured and spirometry will be performed, then subjects will undergo sputum induction. They will be instructed to begin the study drug the evening of the visit, then take it every 12 hours for a total of four doses (the last dose being taken the morning of O₃ exposure). They will arrive on the exposure day and undergo baseline measurements including venipuncture, spirometry, and NO. Subjects will then undergo O₃ exposure, followed by mucociliary clearance, venipuncture, and induced sputum. Subjects will return to the research lab the next morning for a 24 hour follow up. Subjects will have a 3 week-3 month washout and repeat the procedures during the second treatment period, with placebo or yT, depending on randomization.

Subjects will be queried at all visits for any unexpected or adverse events, general health status, medication and supplement use, and for any recent injections.

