vital signs the subject will be shown the treadmill and instructed in proper and safe use. The settings will be increased until the desired minute ventilation is reached. A urine pregnancy test will be repeated on those for whom it is applicable. Vitals signs, including temperature HR, RR, BP, and SpO₂, will be collected before and after treadmill exercise. Spirometry will be performed before exercise begins. Subjects will exercise for 15 minutes, during which time the treadmill will be adjusted to the subjects comfort and to reach the desired minute ventilation. They will then rest for 15 minutes, followed by another 15 minute exercise period to confirm the degree of exercise and the treadmill settings. Subjects will be monitored with cardiac telemetry during the treadmill period, and vital signs will be measured after exercise is complete.

A baseline MCC scan, including a transmission scan, will be completed following the treadmill training. (Full description in section f.)

Nasal epithelial lining fluid (ELF) samples will be obtained from both nares. Nasal epithelial cells (NEC) will be obtained from the right nare.

Subjects will be required to return to the research lab 24 hours after the baseline MCC for a 30 minute follow up scan. (V0b).

III. DOSING:

(Visit 1 and 4)

At Visit 1, subjects will be randomized to receive either active gamma tocopherol or safflower oil placebo. Visit 1 must occur within one month of the baseline visit. Visit 1 may be combined with Visit 0a.

1. Vitals signs will be measured.
2. Urine pregnancy test will be performed on all women of childbearing potential.
3. Spirometry will be performed.
4. Exhaled NO will be measured.
5. Sputum induction will be performed.
6. Subjects will be given study drug prepared by the Investigational Drug Service and instructed to take the first dose of study drug the evening of the visit, 2 days prior to the planned exposure. The second dose will be taken 12 hours later, in the morning on the day prior to the exposure. Dose three will be taken 24 hours after the first dose. The final dose will be taken on the morning of the exposure, 12 hours after dose 3.

IV. OZONE CHALLENGE (after 4 doses of study drug)

(Visit 2 and 5):

Pre-Exposure

1. Urine pregnancy testing if applicable
2. Vital signs
3. Ozone Symptom questionnaire
4. Exhaled NO measurement
5. Spirometry
6. Subject will undergo brief physical examination prior to exposure

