- (2) Analyzer Calibration System. This consists of equipment to provide accurate calibration of the gas analyzer;
- (3) Analyzer Alarm System. Comprises computer software which controls alarms (both sound and visual (light) warnings) and gas shut-off valves.

Description of the Manufacturing Process

The ozone delivery system comprises the following components:

Gas supply bottles and manifolds in the bottle house with oxygen cylinders;
Gas delivery panels;
Gas injection system;
Ozone generator;
Deionized water system;
Computers and computer interfaces.

Stainless steel gas plumbing is used to deliver oxygen to the pollutant delivery system on demand. Mass-flow controller precisely control the amount of oxygen that is supplied to the zone generator and subsequently mixed with facility makeup air. To ensure that the flow of oxygen is not interrupted, each gas manifold (equipped with a pressure regulator) will automatically change from one bank of cylinders to another. The line pressure, of approximately 50 psig, is monitored by a computer. Deionized water is used to humidify the air.

f. Observations and Measurements

- 1. Primary Endpoints:** The primary efficacy endpoint (airway neutrophils/mg in the sputum) will be assessed by post-O₃/pre-O₃ ratio of log sputum PMNS/mg, comparing the ratios during the placebo treatment to the active treatment arms.
- 2. Safety measurements:** Symptom scores, lung function tests, PT and aPTT and platelet counts will be assessed as safety measures. Tocopherols in high doses may rarely have an effect on coagulation.
- 3. Exploratory Endpoints:**

Cytokines and other proteins at baseline and in response to ozone: We will examine sputum and plasma samples for levels of inflammatory cytokines, including (but not limited to) GM-CSF, IL-1 β , IL-4, IL-5, IL-6, IL-8, IL-10, IL-13, RANTES, eotaxin and TNF α . Also to be examined are metalloproteinases, mast cell tryptase, eosinophil cationic protein and eosinophil derived neurotoxin. CRP will also be measured at baseline and 24hr post-exposure.

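### The primary sputum comparison uses the pre-ozone value only through a fixed ratio or change; estimating its slope from the same-period pre-dose sample could recover useful power

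*SAP*

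**What the plan says.** **Outcome.** Protocol section f.1 defines the primary endpoint as the post/pre-ozone ratio of log PMNs/mg, "comparing the ratios during the placebo treatment to the active treatment arms". Section d (Design of Study) says that continuous variables, with sputum PMNs among its examples, "will be assessed using the difference (delta) from baseline". The SAP's own sentence reads "will be assessed using the difference pre O₃ values after" active and placebo dosing, and contains no clear post-ozone term.

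**Test.** After the graphical look at period and treatment effects, the SAP states: "These observations will be tested with a paired t-test or Wilcoxon signed rank test". No covariate is attached. The mixed model comes later: "As an alternative analysis approach, regression modeling techniques will be employed to assess genotype effects". It is meant to "account for the influence of gender, race, BMI" and GSTM1 genotype, and no other covariate is named.

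**Sputum schedule.** Protocol Outline III (Dosing, Visits 1 and 4) lists "Sputum induction will be performed" before study drug is handed out, and the visit table marks sputum at V0, V1, V2, V4 and V5. The August 2016 summary of changes explains the Visit 1 and 4 samples partly as extra baseline data on the primary endpoint. The Observation Schedule in section f mentions sputum only at screening and six hours after each exposure.

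**The concern.** A ratio or a change score decides in advance how strongly the pre-ozone value counts. If the pre-dose sputum in a period predicts the post-ozone sputum in that period only moderately, subtracting or dividing by it in full brings its noise into the treatment contrast. Estimating the slope lets the data set that weight.

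The covariates that are named cannot do this job. Gender, race and BMI are the same in both of a subject's periods, so as main effects they cancel from the treatment contrast when both periods are complete. The pre-dose sputum does vary between periods. It is scheduled, and no analysis names it as a covariate.

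Power for the primary endpoint is at stake, in a trial capped at 32 volunteers and with little power in reserve.

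**Working it through.** **Inputs.** From Sample Size Estimates (section d): the ratio has SD 0.225 on placebo and 0.206 on fluticasone, with means 1.205 and 1.005. The supplement is assumed half as effective, so the effect is 0.5 × 0.200 = 0.100. The correlation between active and placebo responses is 0.5, power 0.80, alpha 0.05, n=29, inflated to 32.

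Assumed, because the documents do not give it: rho, the within-subject correlation between the period-specific pre and post deviations. It is not the planning correlation of 0.5, which links the responses under the two treatments.

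**Step 1: the plan's own figure.**
- SD of the paired difference = √(0.225² + 0.206² − 2×0.5×0.225×0.206) = 0.2161.
- One-sided normal approximation: n = [(1.645 + 0.842) × 0.2161/0.100]² = 28.9, so 29. This reproduces.
- Two-sided: n = [(1.960 + 0.842) × 0.2161/0.100]² = 36.7, so 37.
- Two-sided paired t power is 67% at n=29 and 72% at n=32.

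**Step 2: subject-level covariates.** In simulated crossovers with 32 complete pairs, adding sex, BMI and race left the treatment estimate and its standard error unchanged to five decimals (for example −0.17099, SE 0.03989, both ways). With three or six subjects missing period 2, the standard error moved by about 1% or less, in either direction.

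**Step 3: variance.** Let pre and post deviations each have variance s² and correlation rho, with a separate baseline in each period.
- Contrast of changes: 2s² + 2s² − 4·rho·s² = 4s²(1 − rho).
- Contrast adjusted with a known slope: 2s²(1 − rho²).
- Ratio: (1 − rho²) / [2(1 − rho)] = (1 + rho)/2.
- Cost of estimating the slope: about 1 + 1/(n − 4), which is 1.04 at n=29 and 1.036 at n=32.

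**Step 4: power.** Take 0.2161 as the SD of the change contrast. The noncentrality is 0.100 × √29 / (0.2161 × √factor), with 26 degrees of freedom and two-sided 5%.

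| rho | (1+rho)/2 × 1.04 | noncentrality | power, n=29 |
|---|---|---|---|
| change score | 1 | 2.49 (28 df) | 67% |
| 0.25 | 0.65 | 3.09 | 84% |
| 0.50 | 0.78 | 2.82 | 78% |
| 0.75 | 0.91 | 2.61 | 71% |
| 0.90 | 0.99 | 2.51 | 67% |

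Simulation with a period term agrees with these to within a percentage point. At n=32 the same calculation (factor 1.036, 29 df) takes power from 72% to about 88%, 82% and 76% at rho 0.25, 0.50 and 0.75.

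**Step 5: if one screening sample served both periods.** A shared baseline cancels from the difference of two changes, leaving only the two post-ozone samples. Adjusting for the Visit 1 and 4 values then compares with a post-only contrast. The simulated variance ratios at n=32 are 1.04, 0.99, 0.78 and 0.20 at rho 0, 0.2, 0.5 and 0.9. The gain now rises with rho instead of falling, and at rho 0 there is a small loss.

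**The case against.** **The pre-ozone value is already in the analysis.** This stands. A reader might infer that the plan ignores baseline; it does not. Baseline is the denominator of the primary ratio and the subtracted term elsewhere, and the planning SDs are SDs of that ratio, so n=29 already allows for its noise. Nothing here makes the planned contrast biased or invalid.

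**The mixed model is not the main treatment test.** This also stands. A reader might infer that the sponsor adjusts for gender, race and BMI in the hope of sharpening the within-subject contrast. The SAP presents that model as an alternative aimed at genotype effects, a between-subject question where such covariates can matter, so their presence is no fault.

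**The four-sample variance is conditional.** This stands in part. The visit table and Protocol Outline III support a sample in each period, but the Observation Schedule does not list one, and no passage states which sample is the baseline.

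**The scale differs.** This stands. For a ratio of logs the implied baseline slope is roughly the mean ratio (1.205 on placebo, 1.005 on fluticasone), so it is not exactly 1. The effect and SD come from the ratio scale, so the powers do not carry over exactly to a model of log counts.

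**The gain is neither free nor assured.** This stands. The slope costs 3-4% of variance, and rho is unknown. Against a change score, however, adjustment shows no material loss at any rho examined, up to 0.9.

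**Conclusion.** The point holds as one of efficiency and is worth acting on. The primary sputum comparison fixes the form in which baseline enters, and no analysis estimates a slope on the same-period pre-dose value. Under the stated assumptions, two-sided power at n=29 would rise by about 17, 11 and 4 percentage points at rho 0.25, 0.50 and 0.75, and would not change at 0.9.

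Three assumptions carry this result: the Visit 1 and 4 sputum is the baseline for its own period; the log change behaves like a change score with equal pre and post variances; and rho lies in the range shown. The power figures are approximate because their inputs are on the ratio-of-logs scale.

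The documents do not support the stronger reading that precision is being discarded at no cost and on every scale. Nor does the point extend to every endpoint. Mucociliary clearance has a single baseline scan in the visit table, which is shared by both periods.

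**What to change.** 1. Reconcile the Observation Schedule in section f with Protocol Outline III and the visit table on when baseline sputum is taken, and name the baseline sample for each period.
2. State the post-ozone outcome explicitly in the SAP.
3. For sputum PMNs, make the primary analysis a model of log post-ozone PMNs/mg with treatment, period, random subject and the same-period pre-dose log PMNs/mg (Visit 1 or 4). Enter that baseline as the subject mean plus the within-subject deviation, so that the between-subject slope does not leak into the treatment contrast.
4. Keep the unadjusted ratio or change as a sensitivity analysis.
5. Do not use pre-exposure values from Visits 2 or 5 as baseline, since they are taken on study drug and may already carry a treatment effect. Do not apply the change to mucociliary clearance.

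**Cost.** No new data are needed if the visit table is followed. The model spends one or two degrees of freedom. The primary test is replaced, and its scale moves from a ratio of logs to an adjusted log difference, so the change has to be specified before unblinding and the sample-size rationale restated on the new scale.
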